5.1 Accrual of the Study

Accrual will be summarized by study site, providing the overall rate of accrual over calendar time. The actual rate and projected rate of accrual will be displayed in a graph (the projected rate assumes uniform accrual over time).

6 Study Flow CONSORT Diagram

A description of participant flow will be provided (see appendix 1). The diagram will describe study status from screening to the end of the study. At each stage, reasons for persons not moving forward will be summarized by frequency and category. The diagram will include the following information:

- Number and reasons for those who screen failed
- Number of participants who completed the Month 6 assessments
- Number of participants who completed the Month 12 assessments
- Number and reasons for participants who discontinued study before the Month 12 assessments

7 Evaluation of Demographics and Baseline Characteristics

Tables will summarize the ITT Sample at baseline, including demographics and medical history. Tables will also summarize the mITT and Completers Samples. Descriptive statistics will be presented as N, mean, standard deviation, minimum, 25th quartile, median, 75th quartile and maximum for continuous variables and frequency tables (row, column percentages) for categorical variables. Corresponding box-whisker plots and histogram plots will also be provided.

8 Statistical Analysis

8.1 Overview of Statistical Approach

In our one-group pretest-posttest design the major interest is within-person change in the primary and secondary outcomes over time (response variables) in the presence of one or more explanatory variables that are categorical or continuous. The data will be analyzed using a mixed model for repeated measures approach (MMRM)⁴. Example R code using the 'nlme' and 'emmeans' statistical packages is given by:

```
mdl = temp_data |>
  gls(Score ~ factor(Time) + Age + Sex + Education,
      na.action = na.omit, data = ,
      correlation = nlme::corSymm(form=~Time |Site/Identifiers),
      weights = varIdent(form = ~1|Time))
emmeans(mdl, ~Time, contr = "pairwise")
```

This approach will treat sites and participants as random effects, while observational time and their characteristics such as sex, age and education as fixed effects. Potential effect modifications will be examined using this MMRM approach with variable selection based on Akaike/Bayesian information criterion. The MMRM approach effectively handles missing data, with the assumption that data are missing at random. In this approach, information on missing observations is recovered from the observed outcomes via the within-patient correlation structure. In contrast to the flawed method of last observation carried forward⁵, which uses only one data point, a MMRM analysis uses all the available data to compensate for the data missing on a particular patient.

However, because there is missing data at baseline for certain outcome measures—including the primary outcome because of a technical issue in the measure administration—the MMRM approach on the observed data will not provide inferences on the intention-to-treat (ITT) sample. This is because the MMRM excludes all individuals without at least one measurement of the outcome of interest. To address this issue, multiple imputation of missing data will be undertaken prior to fitting the MMRMs. Forty data sets will be imputed by chained equations (that is, fully conditional specification) using the R package 'mice'⁶ using predictive mean matching (continuous variables), polytomous logistic regression (unordered factors), and logistic

regression (binary factors) following 40 iterations of a Gibbs sampler for each imputed data set. The imputation model will include all time-varying primary, secondary and exploratory outcomes, as well as age, sex, education, racial/cultural background, cognitive diagnostic group, and study site. The sequence of missing data imputation will be ordered from the variable with the smallest percent missing to the variable with the most percent missing. A seed will be specified so that the imputation solution is reproducible.

The quality of the imputed values will be assured by evaluating the distribution of imputed values and examination of trace plots for proper mixing and absence of spikes in the iterations. Subsequent analyses will be conducted on each of the imputed data sets with estimates then being pooled using Rubin's rule ⁷ and degrees of freedom calculated using the Barnard-Rubin adjustment ⁸.

The primary analysis sample will be the ITT sample, i.e., participants with at least one outcome measure will be included in the analyses. As noted above, this will be achieved by fitting MMRMs on the multiply imputed data. As sensitivity analyses, the MMRMs will be fit to the observed data from the mITT and Completers samples. Sex-stratification will be used in analyses as appropriate.

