8.3 Brain Health Pro (BHPro) Intervention

The BHPro Intervention is a 45-week, multidomain, web-based formal educational program designed to increase dementia literacy, foster engagement, and convey best available evidence for lifestyle changes that can mitigate dementia risk. The program was developed as a collaborative effort by CCNA investigators with recognized expertise in the program's content areas, along with input from older-adult citizen advisors. The program was refined and updated based on feedback from focus-groups and a 3-month pilot study to assess usability and accessibility.

Participants will receive instructions on how to register and participate in the program at the remote baseline study visit.

8.3.1 *Program Content*

Participants will register on the BHPro website and obtain a personal password. Participants will need to provide a valid e-mail address and password in order to login and participate in BHPro. Participants will also be asked to enter a preferred name (this can be a first name or nickname), which they will be referred to as throughout their participation in the program. Name and e-mail address will not be included in the study data set. All data from BHPro will be de-identified and linked to the LORIS PSCID prior to being included in the CTU database. Registration will also include viewing a brief video explaining the program, demographic questions and lifestyle questionnaires including general questions related to socio-demographic profile, health, and lifestyle.

BHPro is organized into the following 8 content modules:

1	Motivation, self-efficacy, positive health, dementia, environment vs genetic risk, cognitive aging and healthy lifestyle, medication
2	Physical activity
3	Cognitive engagement
4	Diet
5	Sleep
6	Social and Psychological Health
7	Vascular health
8	Vision and hearing

The program content is provided progressively to deliver new weekly content (i.e. module chapters) of approximately 40 minutes. Participants will have access to new content on 4 modules each week (10 minutes/module; alternating every 2 weeks) through an email push notification, as an approach to maintain interest. Participants will be invited to visit the web site at their own rate but encouraged to spend a minimum of 40 minutes/week on the program.

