13.0 STATISTICAL CONSIDERATIONS

13.1 Sample Size and Power

With a baseline (t1) sample size of 350 participants and an anticipated 20-30% range of drop-out rates, we will have between 245 (with 30% dropout) and 280 (with 20% dropout) completed participants at t2 (end of intervention). All calculations are for 80% power and 5% two-tailed alpha. We considered small ($d=0.2$) and medium ($d=0.5$) Effect Sizes for 4 different t_1-t_2 correlations ($r_{t_1-t_2}$) in the primary outcome variable: $r=0.2, 0.3, 0.4$ and 0.5 . A final sample of $n=280$ will allow us to detect an $ES \geq 0.2$ if $r_{t_1-t_2} \geq 0.3$. A final sample of $n=245$ will allow us to detect an $ES \geq 0.2$ if $r_{t_1-t_2} \geq 0.4$ (please see Table 1 for required sample sizes, and Appendix 4 for supporting formulae).

Table 1: Required sample size to detect $ES = 0.2$ or 0.5 across a range of $r_{t_1-t_2}$ with statistical power = 0.8 and two-tailed alpha error = 0.05.

Effect Size (ES)	$r_{t_1-t_2}$	n
0.2 (small)	0.2	316
	0.3	277
	0.4	238
	0.5	198
0.5 (medium)	0.2	53
	0.3	46
	0.4	40
	0.5	34

It is estimated that approximately 50% of participants will own a smartphone with internet access appropriate for use of the MyCogHealth mobile cognitive assessment (n=175) and an additional 150 will be provided with Android devices (total approx. n = 325).

CTU will provide 120 Axivity devices and 60 EEG headbands to be used for the duration of this study, which should allow for all participants to participate in recordings at Baseline and Month 12. Devices will be centrally distributed from SRI to participants.

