 - i. Levels of engagement (i.e. percent of chapters completed), ratings of satisfaction, and dropout rates from the intervention
 - ii. Levels of engagement in the program as a function of individual characteristics and risk profile
 - iii. Levels of engagement as a moderator of within person change in outcomes.
 - iv. Association between change in modifiable risk factors and change in cognition
- D.** To develop a successful comprehensive national recruitment plan to fully enroll the PTC with engagement stakeholder groups including participants, citizen advisors, and community partners

3 Power and Sample Size Determination

Sample size/power calculation was done based on effect size for one-group pre-/post-design. According to Becker, the effect size ¹ for such a design should be defined as, assuming the standard deviation (SD) at pre- and post-test are equal,

$$ES = \frac{\text{mean change}}{\text{SD baseline}} = \frac{\text{mean change}}{\text{SD change} / \sqrt{2(1 - r)}}$$

where r is correlation between pre- and post-scores. Note that

$$\text{var}(\text{mean change}) = 2\text{var}(\text{baseline})(1 - r)$$

Sample size can then be determined based on the following test statistic

$$T = \frac{\text{mean change}}{\text{SD change}/\sqrt{n}} = \frac{\text{ES}}{\sqrt{2(1-r)/n}}$$

i.e., the corresponding sample size formula for 80% power at 5% significance level to detect ES is given by

$$n = \frac{(1.96 + 0.84)^2}{(\text{mean change}/\text{SD change})^2} + 2 = \frac{(1.96 + 0.84)^2}{\text{ES}^2/[2(1-r)]} + 2$$

Note that plus 2 ($\approx 2 \times 1.96^2$) is to approximate Z-test with sample size for t-test².

Therefore, the sample sizes for detecting small and moderate magnitudes of ES³ at 2-sided 5% significance level with 80% power are given below for values of correlation r

ES	r	n
0.2 (small)	0.2	316
	0.3	277
	0.4	238
	0.5	198
0.5 (medium)	0.2	53
	0.3	46
	0.4	40
	0.5	34

4 Samples of Interest

- a. **Enrolled Sample:** Includes all participants who consented to screening.
- b. **Intention To Treat (ITT) Sample:** Includes all participants who (1) meet screening criteria (2) and completed at least 1 assessment at baseline.
- c. **Modified Intention to Treat (mITT) Sample:** Includes all eligible participants who (1) have completed at least one assessment for the outcome of interest and (2) registered for BHP.

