- d. **Completers Sample (CS):** Includes all eligible participants who have completed the baseline and 12-month assessment for the primary outcome.

5 Enrollment and Participant Flow

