8.2 Analysis of Primary Outcome

The primary outcome is dementia literacy following participation in the study, as measured by the **Alzheimer's Disease Knowledge Scale (ADKS)**. The ADKS is designed to assess knowledge about Alzheimer's Disease (AD) among laypeople, patients, caregivers, and professionals. This self-report questionnaire contains 30 true/false items. The total score is quantitative and ranges from 0-30, with a higher score indicating better knowledge about AD.

An MMRM will be used to evaluate the primary outcome measure of change over time on the ADKS. This model will examine the effect of time (baseline, 6-month, 12-month), adjusted for baseline characteristics including age, sex, race, cognitive status and education.

Inference on change in ADKS from baseline will be conducted via least squared mean estimates as implemented in the R 'emmeans' package ⁹.

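### Does the SAP leave open which ADKS change from baseline is the primary test, and at what significance level?

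*SAP*

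**What the plan says.** **Analysis.** SAP 8.2 specifies an MMRM for ADKS: "This model will examine the effect of time (baseline, 6-month, 12-month), adjusted for baseline characteristics". It continues: "Inference on change in ADKS from baseline will be conducted via least squared mean estimates". No visit is named and no adjustment is mentioned. SAP 8.1 gives a block labelled as example R code that ends with the call "emmeans(mdl, ~Time, contr = 'pairwise". The call has no adjustment argument and covers all pairs of time points.

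**Sample size.** Protocol 13.1 states that "All calculations are for 80% power and 5% two-tailed alpha" and that "we will have between 245 (with 30% dropout) and 280 (with 20% dropout) completed participants at t2 (end of intervention"). SAP section 3 gives the matching formula for one pre score, one post score and one correlation between them: "the corresponding sample size formula for 80% power at 5% significance level to detect ES is given by" the expression that yields Table 1 of the protocol.

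**Other text on timing.** The Completers Sample in SAP section 4 is defined as follows: "Includes all eligible participants who have completed the baseline and 12-month assessment for the primary outcome". Protocol 8.3 says: "The BHPro Intervention is a 45-week, multidomain, web-based formal educational program". Protocol 4.1 and SAP 8.2 both define the outcome as literacy after taking part in the study, which lasts 12 months.

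**The concern.** Two quantities fit the phrase about change from baseline: Month 6 minus baseline and Month 12 minus baseline. The example call adds a third contrast, Month 12 minus Month 6. The sample size was worked out for one test at 5%. If the analysis ran two or three tests, one of two things could go wrong:

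- With a multiplicity adjustment, power at the planned effect size of 0.2 would fall below the stated 80%.
- Without an adjustment, and with success declared on either change, the chance of a false positive on the primary outcome would exceed 5%.

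The SAP names the interval from baseline to Month 12 for the cognitive composites but not for ADKS. That makes the omission more noticeable for the one outcome that supports the trial's main claim. A choice left open could in principle be made after the results are known.

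**Working it through.** **1. Reproduce the planned sample size.** Inputs from Protocol 13.1 and Appendix 4 and SAP section 3: two-sided 5%, 80% power, ES in baseline SD units, and r between pre and post scores.

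n = (1.96 + 0.84)² × 2(1 − r) / ES² + 2

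- ES 0.2, r = 0.3: 7.84 × 1.4 / 0.04 + 2 = 276.4, rounded up to 277.
- ES 0.2, r = 0.4: 7.84 × 1.2 / 0.04 + 2 = 237.2, rounded up to 238.

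All eight entries in Table 1 reproduce in this way. The completer numbers also agree: 350 × 0.8 = 280 and 350 × 0.7 = 245.

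**2. Power on the natural reading (Month 12 minus baseline, one test, unadjusted).** Paired t-test with noncentrality ES / √(2(1 − r)/n) and n − 1 degrees of freedom.

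- n = 280, r = 0.3: noncentrality 0.2 / √(1.4/280) = 2.828, critical value 1.969, power 80.5%.
- n = 245, r = 0.4: noncentrality 0.2 / √(1.2/245) = 2.858, critical value 1.970, power 81.2%.

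The stated power holds.

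**3. Power if both changes from baseline were tested with Bonferroni (assumed; no adjustment is stated).** Each test is at 2.5%, and the critical value is about 2.25.

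| Completers, r | ES 0.20 | ES 0.23 |
|---|---|---|
| 280, r = 0.3 | 71.7% | 84.1% |
| 245, r = 0.4 | 72.6% | 84.8% |

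At these two design points the loss below 80% is therefore confined to true effects close to 0.2. At ES 0.5, the other effect size in Table 1, power exceeds 99.9% even with 245 pairs, r = 0.2 and Bonferroni over three contrasts.

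Adjusting over all three pairs would give 68.2% and 69.1% (Tukey) or 66.3% and 67.3% (Bonferroni) at ES 0.2. That family includes Month 12 minus Month 6, which is not a change from baseline and so lies outside the inference described in SAP 8.2.

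**4. Family-wise error if either unadjusted change counted (assumed; the rule is neither stated nor excluded).** The correlation between the two contrasts is

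(1 − r01 − r02 + r12) / (2√((1 − r01)(1 − r02))),

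where 0, 1 and 2 denote baseline, Month 6 and Month 12. With each r between 0.2 and 0.5 it runs from 0.20 to 0.69. The bivariate normal then gives 9.6% at 0.20, 9.1% at 0.5 and 8.4% at 0.69. At an assumed 0.8 it is 7.8%.

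**5. Which reading does the text support?**

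- SAP 8.1 describes a single-group design with one measurement before and one after the intervention, so there is one change.
- The outcome is literacy after participation. With a 45-week program in a 12-month study, Month 6 falls during participation.
- Protocol 13.1 places t2 at the end of the intervention.
- The Completers Sample requires the baseline and 12-month ADKS and makes no mention of Month 6.
- The 8.1 code is a generic template. It leaves out race and cognitive status, which 8.2 requires, so it is not the primary model as specified.

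Every pointer leads to Month 12 minus baseline, and none to Month 6 as a primary time point.

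**The case for a change.** The strongest opposing argument is that pointers are not a rule. The Completers Sample serves only a sensitivity analysis, and the t2 definition sits in the sample-size section. Even with Month 12 accepted, the SAP does not say whether its p-value is adjusted when the template produces it as one of three, or how an adjustment would work after pooling over 40 imputed data sets. One sentence would settle this at no cost.

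Part of this stands: the sentence is absent, and adding it would do no harm. It does not show that the plan leads an analyst astray. With one change in the sample size, one significance level and no stated correction, silence most naturally means a single unadjusted test, and that test delivers what was planned. Writing a no-adjustment setting into the 8.1 template could also do more than intended, because the same approach serves self-efficacy, attitudes, lifestyle and cognition.

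One caution applies to the power figures. SAP 8.1 reports missing baseline ADKS from a technical fault, so observed pairs could fall below 245. With an assumed 220 pairs at r = 0.4, unadjusted power would be 76.9%. That is a missing-data matter, which the plan addresses by multiple imputation; naming the contrast would not alter it.

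**Conclusion.** The concern does not call for a change. It is correct that no sentence names the primary ADKS contrast or an adjustment, but the documents together leave little doubt that it is Month 12 minus baseline. On that reading the planned error rate and power hold: two-sided 5%, with 80.5% and 81.2% power at the two design points.

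The adverse figures, about 72-73% power or 8-10% family-wise error, each depend on a rule that the documents do not contain. The power loss also disappears at these design points once the true effect is about 0.23 rather than 0.20. The powers treat the comparison as a simple paired test on 245-280 pairs and model neither the covariates nor the imputation. The sample size stands. This is missing detail that competent analysts would fill in the intended way.

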	
With an initial t1 sample size of 350 participants and an anticipated 20-30% range of drop-out rates, we will have between 245 (with 30% dropout) and 280 (with 20% dropout) completed participants at t2 (end of intervention). All calculations are for 80% power and 5% two-tailed alpha. We considered small ($d=0.2$) and medium ($d=0.5$) Effect Sizes for 4 different t1-t2 correlations (r_{t1-t2}) in the primary outcome variable: $r=0.2, 0.3, 0.4$ and 0.5. A final sample of $n=280$ will allow us to detect an $ES \geq 0.2$ if $r_{t1-t2} \geq 0.3$. A final sample of $n=245$ will allow us to detect an $ES \geq 0.2$ if $r_{t1-t2} \geq 0.4$. We are aiming to recruit 50% women to allow for later stratification of analyses to assess for sex differences.
 
Statistical Approach:
 
In our one-group pretest-posttest design the major interest is within-person change in the primary and secondary outcomes over time (response variables) in the presence of one or more explanatory variables that are categorical or continuous. The data will be analyzed using a mixed model for repeated measures approach (MMRM). This approach will treat sites and participants as random effects, while observational time and their characteristics such as sex and age as fixed effects. Potential effect modifications will be examined using this MMRM approach with variable selection based on Akaike/Bayesian information criterion.
 
A more detailed and formal statistical analytic plan (SAP) will be developed and finalized during the study. The SAP will include detailed descriptions for evaluating our study outcomes including BHPro, cognition, physical activity and sleep, and recruitment metrics.

--	---

STUDY SCHEMATIC
Phase A: Platform Trial Cohort and Brain Health Support Program Intervention

[figure not shown]

TABLE OF CONTENTS

LIST OF ABBREVIATIONS	14
1.0 INTRODUCTION	16
1.1 BACKGROUND	16
1.2 RATIONALE	18
2.0 STUDY DESIGN	19
3.0 STUDY GOAL AND AIMS	19
3.1 OVERALL GOAL	19
3.2 AIMS	19
4.0 OUTCOME MEASURES	20
4.1 PRIMARY OUTCOME MEASURE	20
4.2 SECONDARY OUTCOME MEASURES	20
4.3 EXPLORATORY OUTCOME MEASURES	20
5.0 ETHICS AND REGULATORY CONSIDERATIONS	21
5.1 GOOD CLINICAL PRACTICE	21
5.2 INSTITUTIONAL REVIEW BOARD (IRB) / RESEARCH ETHICS BOARD (REB)	21
5.3 ELECTRONIC INFORMED CONSENT PROCESS	22
5.3.1 E-Consent Process	22
5.4 PARTICIPANT CONFIDENTIALITY	23
5.5 POTENTIAL RISKS AND BENEFITS ASSOCIATED WITH THIS STUDY	23
5.5.1 Potential Risks	23
5.5.2 Potential Benefits	24

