8.4.2 Effect of dose (number of chapters completed in BHPro)

Fall-off in use of the program as time on study increases will be monitored, and Cox regression with time-varying covariates will be used to investigate the extent to which a decrease in engagement with BHPro provides an early warning for risk of study dropout.

The effect of dose will be assessed using regression models with restricted cubic splines to allow for non-linearity in the association of the number of chapters completed within the BHPro program (a measure of dose) and dropout status.

8.4.3 Change in modifiable risk factors following participation in the study, as measured by **BHPro Lifestyle Risk Questionnaires**.

Each lifestyle questionnaires includes a quantitative total score.

Physical Activity: The International Physical Activity Questionnaire-Short Form is a brief 7-item self-report measure that captures types of and intensity of physical activity and sitting time. The total score is calculated by summing the accrued number of points assigned per question. The total score ranges between 0-9, with a higher score indicating more physical activity.

Cognitive Engagement: A 6-item questionnaire assessing types and duration of cognitively engaging activities. The total score is calculated by summing the accrued number of points assigned per question. The total score ranges between 0 and 36, with a higher score indicating more cognitively stimulating activities.

Diet: Shorter 11-item version of the Eating Pattern Self-Assessment Questionnaire developed by CCNA Team 5. The total score is calculated by calculating the accrued number of points assigned per question. The total score ranges between 0 and 22, with a higher score indicating more healthy eating habits.

Sleep: Brief 8-item questionnaire developed by BHPro sleep module content leads that assesses sleep duration, sleep patterns, and difficulties and daytime fatigue over the past 3 months. The total score is calculated by summing the accrued number of points

assigned per question. The total score ranges between 1 and 16, with a higher score indicating healthier sleep.

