Mixed effects modelling for burst cognitive testing will be used to disambiguate sources of performance variance within-day, across days, and across burst-to-burst timescales and to include within-person factors (i.e., stress, mood) that influence variation in performance. The data will be evaluated within-person cognitive change, cognitive variation, and differential retest/learning effects at the individual level as potential digital biomarkers.

We will investigate the association of participant demographic characteristics, cognitive status, and BHPro compliance with performance and change in MyCogHealth performance parameters. Exploratory analyses will examine concordance between the MyCogHealth outcome measures and the NTB, Cogniciti BHA, and BHPro Lifestyle Risk factors.

8.4.4.4 Change in performance based on online self-administered cognitive testing with the **Cogniciti Brain Health Assessment (BHA)**.

To evaluate the feasibility of online cognitive assessment, we will examine the number of completed self-administered assessments using the Cogniciti BHA at Baseline, Month 6, and Month 12. We will examine the association of participant demographic characteristics, clinical diagnosis, and BHPro compliance with performance and change from baseline on the Overall Brain Health Assessment Score and each of the subtests of the Cogniciti BHA.

The primary outcome measure for the Cogniciti BHA is the Overall Brain Health Assessment Score. One representative score is calculated from each of the four BHA subtests, and an overall score is calculated from these subtest scores.

1. Spatial Working Memory: Number of responses. This score is the number of

responses (i.e., the number of clicks) required to find all six pairs of shapes, summed across the three trials.

2. Face-Name Association: Recognition accuracy. This is an overall accuracy score for the 24 test items, expressed as a percent. It is calculated as the number of correct hits (i.e., “yes” responses to intact pairs) plus the number of correct rejections (i.e., “no” responses to recombined pairs) divided by the total number of items.

3. Stroop Interference: Incongruent reaction time. The score on this test is the median reaction time, expressed in milliseconds, on the incongruent trials. Of the 30 incongruent trials, reaction times were included only for those trials on which the correct response was given.

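### Effect modification rests on unspecified AIC/BIC selection and sex-stratified fits, so no test with a set error rate shows whether change differs by sex or engagement

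*SAP*

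**What the plan says.** SAP 8.1 gives the decision rule: "Potential effect modifications will be examined using this MMRM approach with variable selection based on Akaike/Bayesian information criterion". The same sentence is in the protocol synopsis (Statistical Approach) and in protocol 13.2. SAP 8.1 then adds: "Sex-stratification will be used in analyses as appropriate". Protocol 13.2.1 says much the same, and the synopsis gives the purpose: "We are aiming to recruit 50% women to allow for later stratification of analyses to assess for sex differences".

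Engagement is a stated aim. SAP Section 2, aim C.iii, reads "Levels of engagement as a moderator of within person change in outcomes".

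The models that are written out contain main effects only. The example code begins "gls(Score ~ factor(Time) + Age + Sex + Education", and for the primary outcome SAP 8.2 says: "This model will examine the effect of time (baseline, 6-month, 12-month), adjusted for baseline characteristics including age, sex, race, cognitive status and education". The GSE model in 8.3.1 has the same form. The dose analysis in 8.4.2 relates "the number of chapters completed within the BHPro program (a measure of dose) and dropout status", so its outcome is dropout and not change in ADKS or GSE. For the burst tests, 8.4.4.3 says "We will investigate the association of participant demographic characteristics, cognitive status, and BHPro compliance with performance and change in MyCogHealth performance parameters", and 8.4.4.4 plans something similar for the Cogniciti test. Neither names a model term or a test. The only explicit interaction with time is in 8.4.6, for sleep and activity measures with burst scores as the outcome.

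**The concern.** AIC and BIC penalise an extra term very differently, and the SAP joins them with a slash and no rule for which one decides. It lists no candidate modifiers and no error rate. Section 8.1 also pools estimates over 40 imputed data sets, which presumes one common model. Selection carried out within each set need not return one.

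For sex, a fit in women and a fit in men give two estimates of change but no estimate or test of their difference.

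At stake are a stated aim (engagement as moderator) and a stated reason for recruiting 50% women. Two competent analysts following the SAP could report different modifiers from the same data.

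**Working it through.** **The plan's own figures.** Protocol Appendix 4 and SAP Section 3 use n = (1.96 + 0.84)² × 2(1 − r)/ES² + 2. For ES 0.2 and r = 0.2: 7.84 × 1.6/0.04 + 2 = 315.6, rounded up to 316. For r = 0.3: 7.84 × 1.4/0.04 + 2 = 276.4, rounded up to 277. All eight tabulated values are reproduced. Completers are 350 × 0.7 = 245 and 350 × 0.8 = 280. These figures concern overall within-person change. Neither document gives a figure for effect modification.

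**How often a null modifier is kept.** A modifier crossed with three visits adds 2 df. AIC keeps it when the likelihood-ratio statistic exceeds 2 × 2 = 4, and BIC when it exceeds 2 ln N. For 2 df, P(χ² > x) = exp(−x/2).

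- AIC: exp(−2) = 13.5%.
- BIC: exp(−ln N) = 1/N. With N as participants, this is 1/245 = 0.41% to 1/350 = 0.29%. With N as observations (three visits), it is 1/735 = 0.14% to 1/1050 = 0.10%.
- For a single contrast (1 df), AIC gives 15.7% and BIC 0.8-1.9%.

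A simulation with 20,000 runs and no sex-by-time effect agreed for 2 df: AIC 14.1%, and BIC 0.3-0.4% counting participants or 0.1-0.15% counting observations.

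**Several candidates.** The documents list none, so the number is an assumption, as is independence. The chance that AIC keeps at least one null term is 1 − (1 − 0.135)^k: 35% for k = 3 and 52% for k = 5.

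**Stratified fits.** Assume a 50:50 split (122.5 or 140 completers per sex), the same true change in both sexes, equal variances and equal r. Power within one sex is p ≈ Φ(ES√n_s/√(2(1 − r)) − 1.96). The chance that exactly one sex is significant is 2p(1 − p).

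| True change | r | p | Exactly one sex significant |
|---|---|---|---|
| 0.2 SD | 0.2-0.5 | 42-66% | 45-50% |
| 0.5 SD | 0.3 | 99.7-99.9% | 0.2-0.7% |

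Example: for ES 0.2, r = 0.3 and 140 per sex, 0.2 × 11.83/1.183 = 2.00. So p = Φ(0.04) = 0.516, and 2 × 0.516 × 0.484 = 0.50.

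**What a direct interaction test can detect.** The detectable sex difference in change at two-sided 5% and 80% power is 2.80 × √(2(1 − r)) × √(4/n).

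- r = 0.5, n = 280: 2.80 × 1 × 0.1195 = 0.34 SD.
- r = 0.2, n = 245: 2.80 × 1.265 × 0.1278 = 0.45 SD.

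For a true difference of 0.2 SD, power is 24-39%, and 80% power would need about 786 to 1256 completers.

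**The case against.** The strongest reply is that these are supporting questions. The trial is powered only for overall change, and information criteria are a recognised way to explore modifiers. BIC is stricter than 5% for a single candidate, so the plan does not always inflate false positives. All of that stands. The fault is an error rate left unset, not one that is always too high.

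Three stronger readings are tempting, and the documents do not support them.

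- A reader might infer that sex differences will be declared by comparing significance between strata. No section says so. Stratified estimates could be set side by side with intervals, and sex could be a candidate in the selection step. What stands is that stratified fits alone supply no test.
- A reader might infer that selection will compare restricted-likelihood fits, because the example code sets no fitting method. Criteria from such fits cannot compare models with different fixed effects. But the code is labelled an example and shows the main-effects fit, not the selection step.
- A reader might infer that engagement is ignored as a moderator. SAP 8.4.4.3 and 8.4.4.4 do plan associations between BHPro compliance and change on two online tests. The gap is the missing test there and the absence of any engagement term in the written ADKS and GSE models.

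The imputation problem is also partial. AIC and BIC are defined for the observed-data sensitivity fits in the mITT and Completers samples. The gap lies in the primary, multiply imputed analysis.

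Finally, a 5% interaction test can also miss real modifiers, as its power above shows. That is a reason to report intervals, not to keep an unstated rule.

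**Conclusion.** The concern holds as a specification fault in secondary and exploratory analyses. The primary ADKS time contrast comes from a main-effects model and is untouched.

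For one null 2-df modifier, the plan allows a false-selection rate from about 0.1% to 13.5%, depending on a criterion and a count of N that it does not name. No rule reconciles selection with pooling over 40 imputed sets. Nothing written tests whether ADKS or GSE change differs by sex or engagement.

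The other figures are illustrations that rest on assumptions. The 35-52% needs three to five independent null candidates. The 45-50% needs equal true changes of 0.2 SD, a 50:50 split, 245-280 completers and r of 0.2-0.5. It lies near the maximum that 2p(1 − p) can take, and at ES 0.5 with r = 0.3 it falls below 1%. Neither should be quoted without those conditions.

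**What to change.** For ADKS and GSE, replace the selection step with prespecified time-by-sex and time-by-engagement interactions, plus time by age, education and cognitive status. Define engagement as percent of chapters completed, as in SAP aim C.i; protocol aim C.i and SAP 8.4.2 use the number of chapters. Fit each interaction in the full sample, with the same model in all 40 imputed data sets. Report the Month 12 interaction contrast with a 95% CI and a Wald test pooled by Rubin's rules, labelled exploratory. Take sex-specific Month 12 changes from that model instead of separate fits. State that a non-significant interaction will not be read as no difference.

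Holm adjustment over the list is optional. At its first step over five modifiers (1%), power for a 0.2 SD sex difference would fall to about 9-18%, which is hard to justify for exploratory questions.

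The cost is SAP wording, a little more code, and matching wording in the protocol synopsis and 13.2 so that the documents agree. Protocol 5.2 requires IRB/REB approval for protocol amendments. No new data are needed. The low power remains, because it comes from the sample size.
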